- b. The Study Intervention Period duration (up to 16 weeks) will depend on the participant's tolerability of the continuous reduction of the infusion duration time. When the participant successfully reaches the shortest infusion duration planned for the cohort which he/she belongs to, he/she will be considered a treatment completer and will not receive any further infusion as part of the study. The study intervention will be permanently discontinued if the participant presents a second IAR.
- c. Participants may have a different number of visits during the Study Intervention Period. Visits 1, 2, 3, 8 and 11 should happen regardless of the number of infusions a participant receives. All other visits are planned but will occur only if the participant does not present any criteria to permanently discontinue the study intervention, such as having a second IAR, or only until the treatment is not considered completed.
- d. Applicable only if the study intervention is administered in this visit. Refer to footnote b.
- e. IAR monitoring will be performed only during the Study Intervention Period which can be shorter than 16 weeks for some participants.
- Note: If a participant is not able to visit the study site for any reason, they should contact the study site by telephone. Adverse event and concomitant medication details may be collected during a telephone call. It may not be possible to collect all clinical laboratory samples or conduct clinical assessments during this time, but any details should be recorded in the source document and electronic case report form (eCRF). If alternative arrangements can be agreed for the sample collection or clinical assessments, the details should be documented in the eCRF.

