To investigate the proportion of participants achieving infusion duration shorter than 90 minutes without experiencing any or the second IAR	Population : Participants with confirmed diagnosis of FD, age 2 to 65 years, Fabrazyme-experienced, treated for at least 3 months without IARs during the most recent 3 infusions.
	Treatment : Fabrazyme 1 mg/kg Q2W up to the rate tolerated (refer to Section 6.2), with oral premedications given 30 minutes prior to each infusion.
	Endpoint : Binary: Participant achieved infusion duration shorter than 90 minutes without experiencing any IAR.
	Intercurrent events: A while-on-treatment approach will be applied. Participants never observed to tolerate any infusion rate will be counted as not achieving the required duration. A treatment policy approach will be applied in case pre-medications are not given as described within the protocol. No action will be taken for this event for the analysis even when pre-medications are not given as described within the protocol.
	Summary measure : Number and % of participants achieving the endpoint.
	Population : Participants with confirmed diagnosis of FD, age 2 to 65 years, Fabrazyme-experienced, treated for at least 3 months without IARs during the most recent 3 infusions.
	Treatment : Fabrazyme 1 mg/kg Q2W up to the rate tolerated (refer to Section 6.2), with oral premedications given 30 minutes prior to each

Objectives	Estimand Description/Endpoints
	infusion. Endpoint: Binary: Participant achieved infusion duration shorter than 90 minutes. without experiencing a second IAR.
	Intercurrent events: A while-on-treatment approach will be applied. Participants never observed to tolerate any infusion rate will be counted as not achieving the required duration. A treatment policy approach will be applied in case pre-medications are not given as described within the protocol. No action will be taken for this event for the analysis even when pre-medications are not given as described within the protocol.
	Summary measure : Number and % of participants achieving the endpoint.
To investigate the number and proportion of participants achieving each infusion duration planned in the study without experiencing any or the second IAR	Population : Participants with confirmed diagnosis of FD, age 2 to 65 years, Fabrazyme-experienced, treated for at least 3 months without IARs during the most recent 3 infusions.

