6.1 Study Interventions Administered

The study has a single arm. All participants will receive 1 mg/kg of body weight of Fabrazyme every 2 weeks at the study site until they reach the shortest infusion duration planned for the cohort they belong to, for up to 16 weeks. The infusion duration and rate will follow the flow presented in Section 6.2.

The participants are not required to stay at the site after completion of the infusion, unless the Investigator considers it medically necessary.

All participants will receive acetaminophen and one antihistamine as non-investigational prophylactic premedication, 30 minutes prior to each infusion. In case of IAR occurrence, participant will receive dexamethasone and montelukast as rescue medication, and both drugs will be given from this time forward as prophylactic premedication, together with acetaminophen and the antihistamine, 30 minutes prior to all further infusions.

The study interventions are presented in Table 3 and Table 4 (for the possible antihistamines allowed as premedication).

Table 3 Study Interventions Administered

Intervention Label	Fabrazyme	Acetaminophen	Dexamethasone	Montelukast
Intervention Name	Recombinant human αGAL (agalsidase beta)	Acetaminophen	Dexamethasone	Montelukast
Intervention Description	Fabrazyme 1 mg/kg Q2W	Acetaminophen	Dexamethasone	Montelukast
Туре	Biological	Drug	Drug	Drug
Dose Formulation	Lyophilized powder for reconstitution	Tablet (for participants >12 years old) or solution (for participants ≤12 years old)	Tablet or solution (alternative only available for participants <16 years old)	Tablet (for participants ≥15 years old), chewable tablet (for participants up to 14 years old) or oral granules (only for participants <6 years old)
Unit Dose Strength(s)	Nominal value of 35 mg to have 5 mg/mL (35 mg/7 mL) after reconstitution with 7.2 mL of sterile water for infusion	650 mg (tablet), or any approved and commercially available solution	7.5 mg (tablet) or any approved and commercially available solution	10 mg (tablet), 5 mg (chewable tablet) or 4 mg (chewable tablet or oral granules)

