15 ENDPOINT EVALUATION

15.1 PRIMARY ENDPOINTS

15.1.1 PRIMARY ENDPOINT VARIABLE(S)

15.1.1.1 SHORTEST INFUSION DURATION EACH PARTICIPANT TOLERATES

The shortest infusion duration tolerated is the actual shortest duration (highest infusion rate) of a completed infusion tolerated by the participant without experiencing a second IAR.

A completed infusion is an infusion during which the entire amount of the study drug planned to be given at the visit has been delivered to the participant via infusion and the question "Was the infusion adjusted from the planned infusion?" is answered either "Infusion not changed" or "Infusion interrupted" on the Fabrazyme eCRF page. If the infusion was interrupted, it will only be considered completed if it was restarted, ie, the stop time of study drug infusion is later than the stop time of infusion interrupted.

An infusion is considered tolerated if it is completed within an actual duration (excluding any interruptions) not exceeding 120% of planned duration, without IAR. If the participant receives several infusions at the same planned duration during the study treatment period, the infusion duration will be considered tolerated if the last infusion with the duration is tolerated. Data for infusion duration tolerated at each visit (scheduled and unscheduled) is captured on the Fabrazyme eCRF pages.

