15.2 SECONDARY ENDPOINTS

15.2.1 SECONDARY VARIABLES

Data for secondary endpoints at each visit (scheduled and unscheduled) are captured on the Fabrazyme eCRF pages.

15.2.1.1 PROPORTION OF PARTICIPANTS ACHIEVING THE SHORTEST PLANNED DURATION OF INFUSION TIME WITHOUT EXPERIENCING ANY OR THE SECOND IAR

To evaluate the objective the following binary variables will be derived for each participant:

- Whether the participant achieved the shortest planned target duration of infusion (20 minutes for participants ≥30 kg and 30 minutes for participants <30 kg) without experiencing a first (ie, any) IAR (yes/no).
- Whether the participant achieved the shortest planned target duration of infusion time (20 minutes for participants ≥30 kg and 30 minutes for participants <30 kg) without experiencing a second IAR (yes/no).

Document: \\ieedc-

Author:

vnasc01\BIOSdata\Sanofi\Fabrazyme\IAB16602\Biostatistics\Documentation\SAP\SAP\Sanofi\Final

Version Number:

Version\lps17726-16-1-9-sap.docx

Version Date: 22Oct2024

Template No.: CS_TP_BS016 Revision 7 Reference: CS_WI_BS005

Effective Date: 01Nov2021

PROTOCOL LPS17726

Analysis Plan Template

Page 46 of 65

15.2.1.2 PROPORTION OF PARTICIPANTS ACHIEVING INFUSION DURATION SHORTER THAN 90 MINUTES WITHOUT EXPERIENCING ANY OR THE SECOND IAR

To evaluate the objective the following binary variables will be derived for each participant:

- Whether the participant achieved infusion duration shorter than 90 minutes without experiencing a first (ie, any) IAR (yes/no).
- Whether the participant achieved infusion duration shorter than 90 minutes without experiencing a second IAR (yes/no).

A participant will be considered a non-responder ie, "No" if they have an initial planned target duration <90 minutes yet fail to tolerate an infusion during the study treatment period with actual duration <90 minutes. Participants with an initial planned target duration <90 minutes will be considered a responder ie, "Yes" if they tolerate at least one infusion during the study treatment period with actual duration <90 minutes.

15.2.1.3 PROPORTION OF PARTICIPANTS ACHIEVING EACH INFUSION DURATION PLANNED IN THE STUDY WITHOUT EXPERIENCING ANY OR THE SECOND IAR

To evaluate the objective the following binary variables will be derived for each participant:

- Whether the participant tolerated the planned infusion duration without experiencing a first (ie, any) IAR (yes/no), calculated separately per each planned infusion duration.

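### SAP 15.2.1.2: the responder rule for participants who start below 90 minutes omits the participant-level IAR condition, so read literally it can score 'Yes' on the no-IAR variable after an IAR

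*SAP*

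**What the plan says.** Protocol Section 3.0 (Table 2) has two secondary endpoints for the 90-minute threshold. The stricter is "Binary: Participant achieved infusion duration shorter than 90 minutes without experiencing any IAR"; the other requires only that there be no second IAR.

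SAP 15.2.1.2 carries both over as separate variables: "Whether the participant achieved infusion duration shorter than 90 minutes without experiencing a first (ie, any) IAR (yes/no") and "Whether the participant achieved infusion duration shorter than 90 minutes without experiencing a second IAR (yes/no"). A paragraph then deals with participants whose initial planned duration is already below 90 minutes. They are 'No' if they fail to tolerate any infusion with an actual duration below 90 minutes, and 'Yes' "if they tolerate at least one infusion during the study treatment period with actual duration <90 minutes". It does not say which variable it serves.

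Four other provisions bear on how the paragraph works:

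- SAP 15.1.1.1 calls an infusion tolerated if it is completed within an actual duration "not exceeding 120% of planned duration, without IAR".
- Where one planned duration is repeated, the same section says "the infusion duration will be considered tolerated if the last infusion with the duration is tolerated".
- After a first IAR the participant receives dexamethasone and montelukast and treatment continues; Protocol 6.1 says "both drugs will be given from this time forward as prophylactic premedication".
- Protocol 1.3, footnote b: "The study intervention will be permanently discontinued if the participant presents a second IAR".

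**The concern.** The responder sentence assigns a final value without repeating either variable's IAR condition at participant level. A specific sentence that ends in 'Yes' is likely to be programmed as it stands, for both variables.

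The stricter variable is the one that describes tolerance of infusions below 90 minutes before dexamethasone and montelukast are added to the premedication. If a participant can have an IAR, receive the added premedication and still count as a success, the variable no longer carries that meaning for those who start fastest. Any error goes one way, from 'No' to 'Yes', and so favours the faster infusion. Two programmers could also reach different counts from the same data.

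**Working it through.** The plan has no figure to reproduce: the study has no sample size calculation and no hypothesis test. The check is one of logic, followed by simple arithmetic on the denominator.

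**Step 1. Is the problem sequence possible?** Take a participant whose planned durations are all below 90 minutes. Infusion 1 gives an IAR. Treatment continues with added premedication (Protocol 6.1). A later infusion is completed on time without an IAR, so it is tolerated (SAP 15.1.1.1). If it repeats the duration of infusion 1, the last-infusion rule means that the earlier IAR does not undo this. The sequence is allowed.

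**Step 2. How is it scored?**

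- Responder sentence: one tolerated infusion below 90 minutes exists, so 'Yes'.
- No-IAR variable as defined in SAP 15.2.1.2 and Protocol 3.0: an IAR has occurred, so 'No'.
- No-second-IAR variable: only one IAR has occurred, so 'Yes'.

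The sentence conflicts with the first variable and agrees with the second.

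**Step 3. How does this depend on the counting period?** SAP 15.2.1.2 does not say whether IARs count over the whole treatment period or only up to the first tolerated infusion below 90 minutes. I enumerated all IAR/no-IAR patterns for n infusions, stopping at the second IAR. Assumptions: all infusions are below 90 minutes, every infusion without an IAR meets the 120% limit, and n = 4, 5 or 9 (9 is the protocol maximum; the others are illustrative).

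- Possible patterns: 1 with no IAR + n with one IAR + n(n−1)/2 with two.
- Sentence disagrees with the no-IAR variable, counting up to achievement: the first infusion has an IAR and a later one is tolerated, n−1 patterns.
- Sentence disagrees with the no-IAR variable, counting over the whole period: all patterns except 'no IAR' and 'IAR at both of the first two infusions', total − 2.
- Sentence disagrees with the no-second-IAR variable, whole period: two IARs and at least one tolerated infusion, n(n−1)/2 − 1.
- Sentence disagrees with the no-second-IAR variable, up to achievement: none, because treatment stops at the second IAR and so any tolerated infusion precedes it.

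| n | Patterns | No-IAR, up to achievement | No-IAR, whole period | No-second-IAR, up to achievement | No-second-IAR, whole period |
|---|---|---|---|---|---|
| 4 | 1+4+6 = 11 | 3 | 9 | 0 | 5 |
| 5 | 1+5+10 = 16 | 4 | 14 | 0 | 9 |
| 9 | 1+9+36 = 46 | 8 | 44 | 0 | 35 |

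These are counts of patterns, not probabilities. They show that the conflict with the no-IAR variable exists on either counting period, and that the no-second-IAR variable is safe only if IARs are counted up to achievement.

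**Step 4. Effect on the reported percentage.** With k misclassified participants out of 14, the shift is 100 × k/14 points: k = 0, 0.0; k = 1, 7.1; k = 2, 14.3; k = 3, 21.4; k = 4, 28.6. The documents do not give k.

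**The case against.** A reader might infer that the rule drops the IAR condition altogether. It does not. It turns on whether an infusion is tolerated, and an infusion with an IAR can never be the qualifying one. What is missing is the condition on the participant's other infusions.

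The paragraph can also be read more kindly, as answering only whether someone who starts below 90 minutes can be said to have achieved that duration. On that reading the two definitions above it still stand with their IAR conditions. SAP 15.2.3 supports this intent: it lists each participant's shortest tolerated duration without any IAR separately from that without a second IAR. This is a fair reading, but the text does not state it, and the literal one is also open.

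The subgroup may be empty. The amendment history (Protocol 10.6, rationale for Section 4.5) names 120 minutes for participants of 30 kg or more and 90 minutes for lighter participants as the shortest possible starting durations. Neither is below 90. This is not conclusive: the titration figures are not shown, Protocol 5.1 sets no limit on pre-study infusion duration, and the SAP, written after that amendment, still provides for starts below 90 minutes.

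An IAR after the first tolerated infusion below 90 minutes may properly leave the value at 'Yes', depending on the counting period. The consequences are limited too: the analysis is descriptive, IARs are tabulated separately, and the listings would let a careful reader find a wrong flag.

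**Conclusion.** The point holds in a narrow form. Read literally, the responder sentence scores 'Yes' on the no-IAR variable for a participant who starts below 90 minutes, has an IAR and later tolerates an infusion below 90 minutes. That contradicts the definition just above it and the protocol endpoint. It is a conflict in the wording with one plausible benign reading, not proof that any participant will be misclassified.

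The size is 7.1 points per affected participant, assuming 14 are enrolled and all are in the denominator. The number affected is unknown and may be 0. It is tempting to infer an overstatement of up to 28.6 points. That would need all four cohort 4 participants, and nobody else, to start below 90 minutes, have an early IAR and then tolerate a later infusion; nothing in the documents supports this, so it is an arithmetic ceiling for that one assumption. Nor is it a defect in itself that the two variables agree for some participants: they should agree for anyone who tolerates an infusion below 90 minutes before any IAR, if IARs are counted up to achievement.

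The SAP should be corrected before database lock, because a stated rule that can give a wrong secondary-endpoint value in the favourable direction is more than missing detail.

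**What to change.** In SAP 15.2.1.2, state that the paragraph on participants who start below 90 minutes settles only the duration component and that each variable's IAR condition still applies. State the IAR counting period explicitly. One workable form, for all participants:

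- No-IAR variable: 'Yes' only if a tolerated infusion below 90 minutes occurred with no IAR at or before it.
- No-second-IAR variable: 'Yes' if a tolerated infusion below 90 minutes occurred before any second IAR.

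If the sponsor confirms that no participant can start below 90 minutes, delete the paragraph instead; the counting period should still be stated.

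The cost is one or two sentences and a derivation line, with no new data. The downside is that the no-IAR percentage may become slightly less favourable.

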15.2.2 Intercurrent Event Handling and Data Imputation for Secondary Efficacy Variable(s)

Refer to Sections 7.2 and 7.3.1.2 for details about intercurrent events and management of missing data.

15.2.3 ANALYSIS OF SECONDARY ENDPOINT VARIABLES

Secondary endpoints will be summarized descriptively, count and percentage, for cohorts 1-4 pooled for the ITT analysis set.

A stacked bar chart split by cohort and planned infusion duration will be provided to summarize objective described in Section 15.2.1.3 and will describe:

- The number of participants who reach the duration without experiencing any IAR.
- The number of participants who have experienced only one IAR.
- The number of participants who have experienced a second IAR

The number of IARs a participant has experienced up to and including the planned infusion duration is displayed.

A listing of participants per cohort presenting their shortest tolerated infusion duration without any IAR will be provided. This listing will also include their shortest tolerated infusion duration without experiencing a second IAR. Responders/Non-responders according to each secondary endpoint will be flagged in listings.

For analysis of the secondary endpoints IARs will be considered separate only when they are occurring in separate infusions. IARs occurring at multiple time points during a single infusion will be considered as a single IAR.

Document: \\ieedc-

 $vnasc01\BIOSdata\Sanofi\Fabrazyme\IAB16602\Biostatistics\Documentation\SAP\SAP\Sanofi\Final\BIOSdata\Sanofi\$

[figure not shown]
Version\lps17726-16-1-9-sap.docx

[figure not shown]
Author: Version Number: Final V1.0

Version Date: 22Oct2024

Template No.: CS_TP_BS016 Revision 7 Reference: CS_WI_BS005

Effective Date: 01Nov2021

Page 48 of 65

15.3 EXPLORATORY ENDPOINTS

15.3.1 EXPLORATORY ENDPOINT VARIABLES & DERIVATIONS

15.3.1.1 PLASMA LYSO-GL3 (NG/ML)

Plasma lyso-GL3 (ng/mL) will be evaluated as a pharmacodynamic biomarker in this study and is also being used as a surrogate endpoint of efficacy that is reasonably likely to predict clinical benefit.

To evaluate the objective the following variables will be derived:

- Change from baseline of plasma lyso-GL3(ng/mL) at each visit
- Percent change from baseline of plasma lyso-GL3(ng/mL) at each visit

15.3.1.1.1 ANALYSIS OF PLASMA LYSO-GL3 (NG/ML)

Values, changes and percent changes from baseline of plasma lyso-GL3 (ng/mL) at each visit will be summarized descriptively for cohorts 1-4 pooled for the ITT analysis set.

During the study treatment period, only results from the samples taken prior to an infusion of the study drug will be considered. During the post treatment period, all samples will be considered. If time is not available and it cannot be determined the assessment was prior to the infusion, then the result will be considered missing.

Refer to Section 7.3.1.3.2 for handling of non-numerical results.

Percent change from baseline per participant and mean for each cohort will be presented in a spaghetti plot. A Listing of participants' observed values, changes and percent changes of Plasma lyso-GL3 (ng/mL) levels at each visit will be displayed per cohort for the ITT analysis set.

Document: \\ieedc-

 $vnasc01\\BIOS data\\Sanofi\\Fabrazyme\\IAB16602\\Biostatistics\\Documentation\\SAP\\SAP\\Sanofi\\Finally and the properties of t$

Version\lps17726-16-1-9-sap.docx

Author: Version Number: Final V1.0

Version Date: 22Oct2024

Template No.: CS_TP_BS016 Revision 7 Reference: CS_WI_BS005

Effective Date: 01Nov2021

PROTOCOL LPS17726

Analysis Plan Template

Page 49 of 65

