1.3 Schedule of Activities

Table 1 Schedule of Activities

		Study Intervention Period: up to 16 Weeks ^b			EOS		
Procedure	Screening (Day -28 to Day 1)	Day 1	Q2W (± 3 days) Except Week 12	At Week 12 (± 3 days) Month 3	At Week 28 (± 3 days) Month 6	Notes	
		W0	W2, W4, W6, W8, W10, W14, W16	W12	W28		
	V1	V2	V3, V4, V5, V6, V7, V9, V10 °	V8	V11		
Written informed consent and participant's assent (when applicable)/assignment of participant identification number	X						
Inclusion and exclusion criteria	X						
Demography	Х					Including but not limited to age, gender, race/ethnicity, and duration of Fabrazyme treatment before entering the study.	
Medical history	X						
Current medical conditions	X						
Urine pregnancy test (only for WOCBC)	X					If a urine test cannot be confirmed as negative, a serum pregnancy test is required.	

		Study Intervention Period: up to 16 Weeks ^b			EOS	
Procedure	Screening (Day -28 to Day 1)	Day 1	Q2W (± 3 days) Except Week 12	At Week 12 (± 3 days) Month 3	At Week 28 (± 3 days) Month 6	Notes
		W0	W2, W4, W6, W8, W10, W14, W16	W12	W28	
	V1	V2	V3, V4, V5, V6, V7, V9, V10 °	V8	V11	
Vital signs and weight	X	X	X	X ^d		Vital signs include body temperature, heart rate, respiratory rate, and blood pressure., which will be assessed before and 1 hour after completion of each study intervention infusion. Refer to Sections 8.2 and 8.4.1.
Plasma Lyso-GL3		X	X	X	X	Blood sampling should be done prior to study intervention infusion. To be done at a central lab.
Serum for anti-agalsidase beta IgG antibody titers		X	X	X	X	Blood sampling should be done prior to study intervention infusion. To be done at a central lab.
Study intervention ^b		X	X	X		
IAR monitoring ^e		←				
AE monitoring		←				
SAE monitoring		←				
Concomitant medication review		←				

- Abbreviations: AE = adverse event; EOS = end-of-study; IAR = infusion associated reaction; IgG = immunoglobulin G; lyso-GL3 = globotriaosylsphingosine; Q2W = every 2 weeks; SAE = serious adverse event; V = visit; W = week; WOCBP = women of childbearing potential.
- a. The Screening Visit (V1) and Day 1 Visit (V2) can take place on the same day. If that occurs, the procedures planned for both visits should be performed only once, and all the screening procedures must be completed prior to the infusion and other study-required procedures.

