2.3.2 Benefit Assessment

The pivotal Phase 3⁷ and extension study⁸ have demonstrated sustained clearance of GL3 from capillary endothelium in the heart, kidney, and skin, as well as from kidney cell types. Renal function remained stable in most participants. However, the effect of Fabrazyme treatment on kidney function was limited in some participants with advanced renal disease. The results also indicate that patients may achieve reduced pain and enhanced quality of life with ERT. In another double-blind, placebo-controlled study with more advanced disease, the rate of clinical events was substantially lower among Fabrazyme treated participants compared to placebo-treated participants, and this result was consistent across renal, cardiac, and cerebrovascular events.

The results of these studies indicate that Fabrazyme treatment at 1.0 mg/kg Q2W provides clinical benefit in key clinical outcomes in patients with early and advanced FD. Because this condition is slowly progressive, early detection and treatment are critical to achieve the best outcomes.

In the open label pediatric study, clearance of GL3 in superficial skin vascular endothelium was achieved in all participants who had accumulated GL3 at baseline.

Since its approval in 2001, many clinical studies and observational data have been published detailing the clinical benefit of Fabrazyme in adults and children with FD ^{9, 10}.

Fabrazyme-based ERT is a life-long treatment and patients require regular intravenous infusions every 2 weeks, which entails a significant burden for them to bear in addition to the symptoms of the disease ¹¹. In this study, additionally to the benefit of continuing treatment with Fabrazyme free of charge during the study, the participants will have the opportunity to benefit from shorter infusions, which will decrease the time committed to treatment and potentially increase their quality of life.

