6.7 Continued Access to Study Intervention After the End of the Study

The Sponsor will not be responsible for study intervention provision after the end of the treatment phase and after the end of the study. Continuing treatment after the end of the Study Intervention Period will be at the discretion of Investigator or treating physician.

The Sponsor will not provide any additional care to participants after they leave the study because such care should not differ from what is normally expected for participants with FD.

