6 GENERAL CONSIDERATIONS

6.1 OBSERVATION PERIODS

- Pre-treatment period: The pre-treatment period is defined from when the participant provides informed consent up to the first dose of study intervention.
- Study treatment period: The study treatment period is defined as the time between the first dose of study intervention to the date of the last dose of study intervention. For Adverse Events, this is known as the Treatment Emergent (TE) period
- Post-treatment period: The post-treatment period is defined as the day after the last dose of study intervention until the last follow-up visit.

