6.3 BASELINE

Unless otherwise specified, baseline is defined as the last observed value, including unscheduled visits, prior to the first date and time of study Fabrazyme infusion after enrolment.

If the last non-missing measurement and reference start date and time coincide that measurement will be considered baseline if the assessment is planned per protocol to take place prior to first administration of study medication during the study treatment period.

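### The pre-infusion sampling rule for lyso-GL3 and ADA is tied to study-drug infusions, so it lapses at Week 28 (and at Week 12 for those already off study treatment) and would accept a sample drawn after a same-day routine infusion

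*SAP*

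**What the plan says.** Four sets of provisions bear on this.

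- **Sample rule in the SAP.** For lyso-GL3 (15.3.1.1.1), during the study treatment period "only results from the samples taken prior to an infusion of the study drug will be considered", and a result that cannot be shown to precede the infusion is treated as missing. The next period has no such condition: "During the post treatment period, all samples will be considered". Section 15.3.1.2.5 repeats both sentences for ADA. Section 6.1 fixes the changeover: "The post-treatment period is defined as the day after the last dose of study intervention until the last follow-up visit".
- **Baseline.** Under SAP 6.3, "baseline is defined as the last observed value, including unscheduled visits, prior to the first date and time of study Fabrazyme infusion after enrolment".
- **Sampling instruction.** In Table 1 of Protocol 1.3, the note on the lyso-GL3 and ADA rows reads "Blood sampling should be done prior to study intervention infusion". Both rows are marked at Week 28; the study intervention row is not. Footnote c adds that "Visits 1, 2, 3, 8 and 11 should happen regardless of the number of infusions a participant receives", so the Week 12 visit also takes place for participants whose study treatment is over.
- **Treatment afterwards.** Protocol 6.7 says "Continuing treatment after the end of the Study Intervention Period will be at the discretion of Investigator or treating physician". Protocol 2.3.2 describes therapy as life-long and says "patients require regular intravenous infusions every 2 weeks".

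When more than one result falls in an analysis window, SAP 6.6.1 selects the one closest to, but before, a study-drug infusion.

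**The concern.** On treatment, the plan regards the order of sample and infusion as important enough to discard a result when that order is unknown. Once study treatment ends, the order is no longer considered, even though the participant may still be receiving the same drug in routine care. Week 28 is the six-month point of both exploratory endpoints (change in lyso-GL3 and in ADA titer). One change-from-baseline series would then follow two standards: a pre-infusion baseline and pre-infusion on-treatment values, but follow-up values that may be taken after an infusion on the same day.

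The Week 28 sample also matters for ADA classification. SAP 15.3.1.2.3 requires positive samples at least 16 weeks apart for a persistent response. Scheduled on-treatment samples after baseline run from Week 2 to Week 16, which is 14 weeks. On scheduled visits, therefore, only Week 28 can complete that interval.

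**Working it through.** The plan has no figure to reproduce: there are no hypotheses (Protocol 9.1) and no sample size calculation (Protocol 9.5, SAP 17). The check is textual, with day counts.

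**1. Which samples fall outside the rule.** The last study infusion is at Week 16 at the latest, so Week 28 comes at least 28 − 16 = 12 weeks after it, and every Week 28 sample is post-treatment. A participant whose last study infusion was at Week 10 or earlier, through completion or discontinuation, is also post-treatment at Week 12. The rationale in the protocol's amendment history gives the earliest completion without an IAR as Week 8 (≥30 kg) or Week 6 (<30 kg), so this will be common if the shortening is well tolerated.

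**2. Whether routine infusions are likely in between.** If dosing every 2 weeks continues, the number of infusions between the last study dose and Week 28 is (gap in weeks ÷ 2) − 1:

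| Last study dose | Gap to Week 28 | Routine infusions in between |
|---|---|---|
| Week 16 | 12 weeks | 5 |
| Week 8 | 20 weeks | 9 |
| Week 6 | 22 weeks | 10 |

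**3. Whether a routine infusion can fall on the visit day.** Week 12 is 12 ÷ 2 = 6 whole cycles after Day 1, and Week 28 is 28 ÷ 2 = 14. If routine dosing stays on the study calendar (an assumption), an infusion is due on the nominal day of each visit. The sample could then be drawn before or after it. The protocol's ±3 days around an aligned schedule covers 7 of the 14 days of a cycle: 0 to 3 and 11 to 13 days after an infusion.

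**4. Whether the analysis windows restrict this.** They do not. In SAP Table C, Week 12 is Days 77–90, or 90 − 77 + 1 = 14 days (one cycle). Week 28 is Days 154–210, or 210 − 154 + 1 = 57 days (57 ÷ 14 = 4.1 cycles). Both admit every day of a 14-day cycle.

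**5. Whether another sentence closes the gap.** Three candidates do not:

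- The missing-if-unknown sentence follows a rule about study-drug infusions, so in context it concerns those infusions.
- Protocol 6.0 defines study intervention as what is given under the protocol. Routine Fabrazyme after treatment ends is outside that definition, and Protocol 6.7 says the sponsor is not responsible for providing it. The Table 1 note therefore does not reach it.
- The selection rule in SAP 6.6.1 needs a study-drug infusion as its reference. Week 28 has none, and Week 12 has none for those already off study treatment.

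**Result.** A sample drawn after a same-day Fabrazyme infusion is excluded while the participant is on study treatment and accepted afterwards.

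**The case against.** The strongest reply is that accepting all post-treatment samples is deliberate. SAP 7.2 applies treatment policy to the exploratory endpoints, so values are used whether or not study treatment was stopped early. That stands as a reason to keep participants who stopped, lapsed or changed schedule. It does not settle the present point, because that section deals with discontinuation and premedication, not with the order of sample and infusion on one day.

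Several limits also stand. The documents allow such a draw but do not say that sites will make it. Sites may extend the Table 1 note to routine infusions, and the Laboratory Manual cited in Protocol 8.3.1 is not available here. Dates of all medication are recorded (Protocol 6.9) and listed (SAP 13.3), and individual lyso-GL3 and ADA values are listed too. Days since the last infusion should therefore be recoverable, although clock time, which decides the same-day case, is not assured. The endpoints are exploratory and descriptive.

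A reader might infer that follow-up samples should be held to a trough, for example 14 ± 3 days after the last infusion. The documents do not support that. The on-treatment rule sets no interval since the previous infusion, so a mid-cycle sample does not breach it, and baseline has no such interval either. The restriction would also be costly. If sampling days were uniform over a 14-day cycle (an assumption), only days 11–14 would qualify, 4/14 = 29%, and 10/14 = 71% of Week 28 values would be lost, about 10 of 14 participants. Those who lapsed or stopped would be removed as well, against treatment policy. The 29% describes a criterion that is not in the plan and does not measure departure from it.

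**Conclusion.** The gap in wording is real and narrow. It exempts every Week 28 sample, and the Week 12 sample of anyone whose last study infusion was at Week 10 or earlier, from the pre-infusion rule. The only draw that the plan's own on-treatment standard would clearly reject is one taken after an infusion on the same day.

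Whether that occurs depends on routine Fabrazyme continuing and on an infusion falling on the visit day before the sample; neither is fixed by the documents. The size of any bias cannot be computed, because the documents give no within-cycle variation for lyso-GL3 or ADA titer. It would therefore go too far to say that the six-month changes will be distorted. Primary and secondary results are unaffected. This is a minor, optional correction, worth making because it is cheap and because, with at most 14 participants, a few mistimed values could move a summary.

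**What to change.** **Protocol, Table 1.** For Visits 8 and 11, word the lyso-GL3 and ADA note so that sampling precedes any Fabrazyme infusion given that day, study or routine. Record the date and time of the last Fabrazyme infusion before the sample.

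**SAP 15.3.1.1.1 and 15.3.1.2.5.**
- Set a post-treatment sample taken after a same-day routine infusion to missing in the by-visit summaries.
- Keep all other post-treatment samples, in line with SAP 7.2.
- List days since the last Fabrazyme infusion beside each Week 12 and Week 28 value.
- State whether a sample excluded from the by-visit summaries still counts for the ADA response categories. Without Week 28, scheduled visits cannot yield a persistent classification.

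**SAP 6.6.1.** Give the selection rule an anchor for windows with no study infusion, for example the target day already shown in Table C.

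**Cost.** One note, one date and time field, and a few lines of SAP text. A few values may move from a summary to a listing. If sampling is already complete, days since last infusion can still be derived from the recorded medication dates. The same-day exclusion can then be applied only where clock times exist, and the SAP should say how same-day cases without a time are handled.
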